9. Study Intervention/ Investigational Product	24
9.1 Investigational Agent	24
9.2 Administration	25

9.3 Criteria for removal from dosing of Lambda.....	Error! Bookmark not defined.
9.4 Storage of Investigational agent.....	25
9.5 Blinding of study participants.....	25
10. Study Location and Infection Control Considerations.....	25
11. Risks and Benefits.....	26
12. Outcome measures.....	26
13. Statistical Considerations.....	27
13.1 Sample Size and Power Considerations.....	27
13.2 Statistical Analysis.....	27
14. Safety Oversight.....	28
14.1 Monitoring Plan.....	28
14.2 Study monitoring.....	28
14.3 Withdrawal criteria.....	29
14.4 Study stopping rules.....	29
15. Protection of Human Subjects.....	29
15.1 Ethical Standard.....	29
15.2 Institutional Review Board.....	30
15.3 Informed Consent Process.....	30
15.4 Participant Confidentiality.....	31
16. Data Management and Monitoring.....	31
16.1 Source Documents.....	31
16.2 Data Management Plan.....	32
16.3 Data Capture Methods.....	32
16.4 Study Record Retention.....	32
17. References.....	33

1. Protocol Synopsis

TITLE: Peginterferon lambda-1a for the prevention and early treatment of SARS-CoV-2 infection

DESIGN: A phase 2b prospective, randomized, single-blind, controlled trial of one subcutaneous injection of peginterferon lambda-1a or placebo for non-hospitalized participants at high risk for infection with SARS-CoV-2 due to household exposure to an individual with COVID-19 and one subcutaneous injection of peginterferon lambda-1a or placebo for non-hospitalized participants with asymptomatic SARS-CoV-2 infection detected at study entry. All participants will be followed for an observation period of up to 10 weeks

DURATION: Participants will be on study for a total of 4 weeks (treatment and observation period).

SAMPLE SIZE: Up to 164 participants will be enrolled in the study for a sample of 110 participants at risk for SARS-CoV-2 infection due to household exposure to an individual with COVID-19 (Prevention Cohort). The treatment cohort sample will be determined by the proportion of asymptomatic persons with SARS-CoV-2 detected at study entry constituting an exploratory cohort.

STUDY CENTER: Johns Hopkins Health System.

POPULATION Household contacts of patients confirmed to have COVID-19 based on SARS-CoV-2 RT-PCR. Consented participants will subsequently enter the treatment or prevention cohorts based on the presence or absence of SARS-CoV-2 on the nasopharyngeal sample obtained at study entry.

Group A: Non-hospitalized, household contacts of individuals with confirmed COVID-19 infection who test RT-PCR negative for SARS-CoV-2 infection at study entry (Prevention cohort)

Group B: Non-hospitalized, household contacts of individuals with confirmed COVID-19 infection who test RT-PCR positive for SARS-CoV-2 at study entry (Treatment cohort).

All participants ≥ 18 years of age who are household contacts of individuals with confirmed COVID-19 infection (within 7 days of diagnosis) without self-report of symptoms of acute respiratory illness (fever, cough or shortness of breath).

At the time of enrollment, the SARS-CoV-2 infection status of the participant will not be known and their inclusion in Group A (Prevention cohort) or Group B (Treatment cohort) will be based on the results of upper respiratory tract sampling at study entry. Participants without detection of SARS-CoV-2 RNA at the time of screening/enrollment will constitute Group A (Prevention cohort) whereas as those with detection of SARS-CoV-2 RNA will constitute Group B (Treatment cohort).

At enrollment into Step 1, all participants in both Group A and B will be non-hospitalized and have a normal blood oxygen saturation by pulse oximetry ($\geq 95\%$) on room air and a respiratory rate of fewer than 25 breaths/minute.

REGIMEN

Enrollment occurs in two Steps. After confirming eligibility, participants are enrolled into Step 1.

Prior to knowledge of infection status, participants will be randomized 1:1 to treatment with peginterferon lambda-1a (Lambda) 180 micrograms by subcutaneous injection one dose (Active Arm) or placebo by subcutaneous injection (Placebo Arm).

Duration of treatment is one week with an additional three week observation period.

Based on the results of SARS-CoV-2 RT PCR testing of upper respiratory tract samples at the time of enrollment into Step 1, persons who test RT-PCR negative at Day 0 will constitute group A.

Participants who test RT-PCR positive for SARS-CoV-2 at entry make up Group B, the treatment cohort.

Group A Prevention Cohort	Day 0	Ratio
Active	Active	1
Placebo	Placebo	1

Group B Treatment Cohort	Day 0	Ratio
Active	Active	1
Placebo	Placebo	1

PRIMARY OUTCOMES

- Group A Prevention cohort: To estimate the proportion of participants with no evidence of SARS-CoV-2 infection at or before day 28
For the purpose of the study endpoint, SARS-CoV-2 infection is defined as any of the following outcomes:
 - SARS-CoV-2 detected in upper respiratory samples at any of day 7, day 14 or day 21; or
 - New finding of serum antibodies (IgA or IgG) against the SARS-CoV-2 spike protein according to validated specifications and performance characteristics before or on day 28.
- Group B. Treatment cohort: Proportion of participants with resolved SARS-CoV-2 infection at Day 14 defined as non-detection of SARS-CoV-2 RNA in two respiratory samples before or on day 14

SECONDARY OUTCOMES

Group A Prevention cohort

- Time to onset of signs and symptoms consistent with COVID -19 (Symptoms: Cough, sore throat, generalized body aches and shortness of breath; Signs Fever >100.4 F, RR >25, SpO2 <95% on room air)
- Hospitalization
- Proportion with treatment-emergent adverse events

Group B Treatment cohort

- Time to onset of signs and symptoms consistent with COVID -19 (Symptoms: Cough, sore throat, generalized body aches and shortness of breath; Signs Fever >100.4 F, Respiratory rate >25, SpO2 <95% on room air)

- Incidence of progressive clinical disease at or before 14 days after enrollment assessed by SpO₂ (determined by home pulse oximetry, when available).
- Hospitalization
- Time to clinical resolution of signs and symptoms consistent with COVID-19 (Among those that develop symptoms)
- Proportion with treatment emergent adverse events

EXPLORATORY OUTCOMES

- Relationship of outcomes with genetic polymorphism related to interleukin-28b
- Compare the rates, levels and duration of SARS-CoV-2 RNA in upper respiratory samples using RT-PCR

[figure not shown]
KEY INCLUSION

- Willing and able to provide written informed consent
- Peripheral capillary oxygen saturation (SpO₂) \geq 95% on room air at screening
- Age \geq 18 years to \leq 80 years

KEY EXCLUSION

- Hospitalized or impending hospitalization at the time of screening
- Symptoms of cough, fever or shortness of breath within 72 hours
- Prior or current treatment with other experimental or approved agents targeting SARS-CoV-2 or SARS-CoV-1
- Positive pregnancy test
- Active autoimmune disease or sarcoidosis (with the exception of controlled thyroid disease)
- Active decompensated liver disease (ascites, encephalopathy)
- Active congestive heart failure
- Hemodialysis or peritoneal dialysis

2. Study Schema

3. Hypothesis and study objective

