Step 1: All participants will be ≥ 18 years of age and will be determined on remote telephonic screening to be household contacts of individuals with confirmed COVID-19 infection. Household contacts are individuals who have lived in the same household for at least 24 hours preceding COVID-19 infection diagnosis in the index patient and who intend to continue to live in the same household for the next 14 days after diagnosis. At the time of enrollment, the SARS-CoV-2

infection status of the participant will not be known. Participants will be enrolled in a 1:1 ratio into Active or Placebo Arms

Step 2: Based on the results of SARS-CoV-2 RT PCR testing of upper respiratory tract samples at the time of enrollment into Step 1, persons who were found to be RT-PCR negative for SARS-CoV-2 at screening/entry will form the study population for the Group A Prevention Cohort.

Step 2 Groups A COVID-19 negative	Day 0		Ratio
Active	Active		1
Placebo	Placebo		1

Participants who test RT-PCR positive for SARS-CoV-2 at Day 0 will not be eligible for Step 2 and will proceed to a follow-up Schedule of Events. These participants make up Group B, the treatment cohort.

Step 2 Group B COVID-19 positive	Day 0		Ratio
Active	Active		1
Placebo	Placebo		1

The primary study population is the participants in the Group A Prevention cohort. However, since the infection status of persons enrolled in Step 1 is not known, there is an opportunity to study the effect of a single dose of lambda or placebo in a population of participants with mild SARS-COV-2 infection (Group B Treatment Cohort).

All participants will have interval follow-up visits until the end of week 4.

6 Selection of Participants

The following criteria must be met at the time of study entry/ Day 0 in order for participants to be enrolled in this study.

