6.1.2.1 Women who are pregnant or lactating

6.1.2.2 Fever or cough or shortness of breath within 72 hours of the screening visit

6.1.2.3 Hospitalization or the need for hospitalization for any reason at the time of screening

6.1.2.4 Prior or current treatment with other experimental or approved agents targeting SARS-CoV-2 or SARS-CoV-1

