6.2.1.1 Absence of SARS-CoV-2 infection at screening/entry visit

7 Schedule of Events

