8.9. Randomization

Randomization will take place on day 0 after screening activities have been performed and the Investigator or designee has determined that the participant is eligible. Day 0 laboratory tests including blood SARS-CoV-2 RT-PCR results are not part of the eligibility criteria and participants will be randomized without this information. Randomization will be built into the study REDCap database. It will not be known at entry/screening whether participants are part of Group A or Group B since their COVID-19 infection status will not be known until entry/screening specimens are processed. All participants will be randomized in a 1:1 ratio to receive Lambda/Lambda (Arm 1) or Placebo/Placebo (Arm 2). Participants who are not eligible for enrollment into Step 2 (will be removed from protocol therapy Single dose of Lambda or placebo) respectively.

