8.12. Serology for SARS-CoV-2

At entry and day 28, all participants will have blood sampled to detect antibodies against the SARS-CoV-2 spike protein (S1 subunit). Testing will be performed at the Johns Hopkins Pathology Laboratory using the commercial Euroimmun antibody assay according to the manufacturer's recommendation. This assay has been validated by the Johns Hopkins laboratory. 6 mL of blood will be collected for each timepoint.

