Participants who are found to be infected with SARS-CoV-2 at baseline (Group B) or who become infected during the course of the study (Group A) will not return to the study site until Day 28 or until criteria for discontinuation of infected status is met per HEIC standards, whichever occurs later. In the event that an interim in-person visit is required to evaluate an adverse event, these participants may be seen in an ambulatory setting equipped for encounters with SARS-CoV-2 infected persons. In the event that participants become hospitalized, study evaluations that coincide with clinical care will be abstracted from the medical record. Research-specific evaluations will not continue in the inpatient setting.

11. Risks and Benefits

Potential Risks of Treatment

Identified risks associated with treatment with Lambda based on nonclinical and/or clinical data, as well as potential class effects, include hepatobiliary toxicity (transaminase elevations with or without hyperbilirubinemia) and injection site reactions; potential risks include neuropsychiatric disorders (including depression), cardiovascular events, immunogenicity/hypersensitivity reactions, autoimmune disorders, elevated amylase/lipase, dermatitis, hypersensitivity reaction, injection site reaction, and reproductive risk. Complete information on preclinical and clinical safety data is located in the Investigator Brochure.

Potential Benefits of Participation

Potential benefits include prevention of infection with SARS-CoV-2 infection or reduction in severity of COVID-19 symptoms. It is not yet known whether Lambda will have any benefit in this population.

Alternatives to Participation

The alternative to participation in this study is routine care and monitoring following close contact with an individual with COVID-19.

12. Outcome measures

12.1 Group A Prevention cohort primary endpoint:

- No evidence of SARS-CoV-2 infection at or before study day 28

For the purpose of the study endpoint, SARS-CoV-2 infection is defined as any of the following outcomes:

1. SARS-CoV-2 detected in upper respiratory samples at any of day 7, day 14 or day 21; or
2. New finding of serum antibodies (IgA or IgG) against the SARS-CoV-2 spike protein according to validated specifications and performance characteristics at or prior to day 28.

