13.1 Sample Size and Power Considerations

The planned sample size for the trial is 164 participants enrolled and randomized in a 1:1 ratio to lambda interferon-1a versus placebo injection. This sample size is based on the expectation that approximately 32.5% of participants who are enrolled have evidence of SARS-CoV-2 at study entry (an intermediate value consistent with the 25 – 40% infection range that we expect for the study outcome in the placebo group), thus around 110 will be will have no evidence of SARS-CoV-2 infection (Prevention Cohort) at enrollment and around 54 participants will have evidence of SARS-CoV-2 infection (Treatment Cohort). The Treatment Cohort represents an exploratory pilot study to provide estimates of antiviral efficacy for early COVID-19. Power estimates for the study are based on the Prevention Cohort and incorporate the following assumptions (multiple credible scenarios are presented):

The primary analysis for the efficacy/prevention of infection with SARS-CoV-2 in the Lambda interferon-1a and the placebo groups using proportional odds model and a two-sided Type I error rate (α) of 0.05. Since participants in both the Prevention and Treatment Cohorts will be dosed after entry, we anticipate that few, if any participants will not start treatment and be excluded from the primary analysis. Further, given the nature of COVID-19, we anticipate low rates of loss to follow-up before the primary endpoint (Day 14). We expect the incidence of new COVID-19 in the placebo group to be between 25% to 40%, thus we will perform calculation for these edge-case scenarios. In addition, we will be offering enrollment to all adults in a household (~2 per household), our analysis sample will be clustered-correlated by household. However, there is no preliminary or published data to model within-cluster correlation. Thus we are modeling scenarios where the effective sample size is as high as 110 individuals, or as low as the number of households of 55. In all scenarios, we are expecting that the cumulative infection fraction for the lambda interferon will be 5%.

Cumulative Infection Percentage in Placebo	Effective sample size	
	N= 110 individuals	N = 55 family clusters
25%	80.1%	36.1%
40%	99.6%	84.0%

We note that we have 80% or greater power (and Type II error rate beta of 0.2 or smaller) in a large range of scenarios.

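### Group A is defined by a negative Day 0 swab alone, so contacts who already carry spike antibodies at entry stay in the prevention analysis and will usually count as successes in either arm

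*Combined protocol and SAP*

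**What the plan says.** **Membership.** The synopsis (section 1, Population) sets Group A by the entry swab: "Participants without detection of SARS-CoV-2 RNA at the time of screening/enrollment will constitute Group A (Prevention cohort". Section 5 (Study Design, Step 2) agrees: "persons who were found to be RT-PCR negative for SARS-CoV-2 at screening/entry will form the study population for the Group A Prevention Cohort". Section 6.2.1.1 gives the only Step 2 criterion, "Absence of SARS-CoV-2 infection at screening/entry visit"; it names no assay, and section 5 supplies RT-PCR. Section 8.9 says that Day 0 laboratory tests "are not part of the eligibility criteria and participants will be randomized without this information".

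**Exclusions.** Section 6.1.2 excludes neither previous COVID-19 nor existing antibodies. Its symptom criterion is "Fever or cough or shortness of breath within 72 hours of the screening visit". The prescreening call in 8.1 covers a longer symptom list.

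**Endpoint.** Under the synopsis and 12.1, a Group A participant is infected if a swab at day 7, 14 or 21 is positive, or on a "New finding of serum antibodies (IgA or IgG) against the SARS-CoV-2 spike protein" by day 28. Section 8.12 provides the serum: "At entry and day 28, all participants will have blood sampled to detect antibodies".

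**Sizing and analysis.** Section 13.1 plans for around 110 people who "will have no evidence of SARS-CoV-2 infection (Prevention Cohort) at enrollment". Section 13.2.1 analyses everyone randomized with a mixed logistic model. Neither it nor 13.2.3 mentions antibody status at entry.

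**The concern.** The primary question is prevention in people not yet infected, and 13.1 describes the cohort that way. The swab rule delivers a wider group. The index diagnosis may be up to 7 days old (6.1.1.4), and nothing requires the index patient to have been the first person infected in the household. A contact infected earlier, without recent symptoms and swab-negative again, can enter Group A with antibodies already present.

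If that contact has both isotypes on Day 0, the antibody limb can no longer be met. Only the swab limb is left. In practice it rests mainly on days 7 and 14, because 12.1 names day 21 but neither 7.2 nor 8.11 schedules a day 21 swab. Most such contacts would be scored as uninfected whatever they received.

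At stake are the quantity that 3.2.1 sets out to estimate (the proportion with no evidence of infection), the absolute difference that 13.2.1 promises to report, and possibly power.

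**Working it through.** **Inputs.** From 13.1: 164 enrolled 1:1, 32.5% swab-positive at entry, about 110 in Group A (55 per arm), placebo infection 25% to 40%, lambda infection 5%, two-sided alpha 0.05, effective sample size 110 down to 55. The share s of Group A already seropositive at entry is **not in the documents**; 10% and 20% are used as assumptions.

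**Step 1: reproduce the plan.** 164 × 0.675 = 110.7 and 164 × 0.325 = 53.3, matching the planned split. Exact power of the two-sided Fisher test, by full enumeration at 55 and 27 per arm, gives 80.1%, 36.1%, 99.6% and 84.0%. These are the four cells of the 13.1 table.

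**Step 2: leave seropositives in.** Take 13.1's rates as applying to seronegative contacts, and suppose seropositive contacts never score an event. Each arm's rate p becomes p(1 − s).

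- 25% vs 5%: 22.5% vs 4.5% at s = 10%, a difference of 18 points; 20% vs 4% at s = 20%, a difference of 16. The planned difference is 20.
- 40% vs 5%: 36% vs 4.5%, a difference of 31.5 points; 32% vs 4%, a difference of 28. The planned difference is 35.
- In the 25% row the placebo proportion uninfected rises from 75% to 77.5% or 80%, and lambda's from 95% to 95.5% or 96%.
- The risk ratio is p₁(1 − s) / [p₂(1 − s)] = p₁/p₂, unchanged at 0.20 in the 25% row.
- The odds ratio in the 25% row moves from 0.158 to 0.162 or 0.167.

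Fisher power:

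| Rates | Effective N | s = 0 (plan) | s = 10% | s = 20% |
|---|---|---|---|---|
| 25% vs 5% | 110 | 80.1% | 73.7% | 65.9% |
| 25% vs 5% | 55 | 36.1% | 29.3% | 22.7% |
| 40% vs 5% | 110 | 99.6% | 98.9% | 97.5% |
| 40% vs 5% | 55 | 84.0% | 76.7% | 67.4% |

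Giving seropositives a 2% chance of a positive swab instead of zero changes the 25%, N = 110 row only to 73.1% and 64.4%.

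**Step 3: remove seropositives.** Rates return to plan and n per arm becomes 55(1 − s): 49.5, taken as 50, or 44. At 25% vs 5%, power is 74.8% or 69.5%. That exceeds leaving them in by 1.1 and 3.6 points, but is still below 80.1%. Keeping 110 seronegative contacts would need a Group A of 110/0.9 ≈ 123 or 110/0.8 ≈ 138, which at 67.5% swab-negative means about 182 or 204 enrolled against 164.

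**Step 4: the other reading of 13.1.** If 25% to 40% and 5% already describe all RT-PCR-negative contacts, seropositives included, the rates need no adjustment and the table in 13.1 stands.

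**Step 5: under the null.** If both arms have rate p, both become p(1 − s) and remain equal. Enumerated Fisher type I error at 55 per arm is 3.0% at p = 25% and 2.7% at p = 20%, both under 5%.

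**The case against.** The strongest defence is that the plan's estimand is coherent. Dosing happens before any Day 0 result is known, so the effect in all swab-negative contacts is a fair question. The endpoint is defined for study purposes as incident infection, and counting only new antibodies deliberately sets aside pre-existing ones. Entry serology therefore does enter the analysis, as the implied comparator for *new*. All of this stands. What is missing is a rule for people already positive at entry, and a cohort definition that matches 13.1's description.

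Several stronger readings are tempting and should not be drawn:

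- *Seropositive contacts are automatic successes.* They can still fail on a swab. Because *new* is not defined by isotype, someone with IgA only at entry and IgG at day 28 might also count as infected.
- *The endpoint contradicts its own name.* It carries its own definition, which leaves out antibodies already present.
- *Only three symptoms in the last 72 hours keep recent cases out.* Section 8.1 screens more widely, and 6.1.2.4 excludes prior treatment targeting the virus. These filters may remove some recently infected contacts, but not those who had no symptoms.
- *The comparison is biased, or chance imbalance invalidates it.* Entry serostatus precedes randomized dosing. Imbalance in any baseline factor is part of the sampling variation that the test allows for.

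The defence is also right that the loss of power depends on how 13.1's rates are read, and that at N = 110 the 40% row barely moves.

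**Conclusion.** The point holds as a mismatch between the population that 13.1 describes and the one that the swab rule selects. It does not threaten validity: there is no bias under the null, no inflation of type I error, and the risk ratio is preserved. The effect is on estimation. The proportion uninfected is raised in both arms relative to susceptible contacts, and the absolute difference shrinks by the factor 1 − s.

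Power is affected only if 13.1's rates refer to seronegative contacts. In that case the 25% vs 5%, N = 110 cell, which sits at 80.1% with no margin, falls to 73.7% or 65.9% at s of 10% or 20%. At 40% vs 5% it stays at 98.9% or 97.5% for N = 110; for N = 55 the planned 84.0% drops below 80%. All of these figures rest on an assumed s and on seropositives rarely or never scoring an event. The documents support neither a particular value of s nor a rate of later positive swabs in such contacts. This is a cheap and worthwhile improvement, not a fundamental flaw.

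**What to change.** In 12.1, 13.1 and 13.2.1, define the Group A primary analysis population as RT-PCR negative **and** spike IgA and IgG negative on the Day 0 samples. Both samples are baseline measurements, so restricting on them after randomization introduces no post-treatment selection; the plan already splits Groups A and B on the same principle. In addition:

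- Define a new antibody finding as conversion from the Day 0 result. For the supporting analysis, say whether IgG at day 28 after IgA alone at entry counts.
- Prespecify the analysis of all RT-PCR-negative participants as supporting, so that swab-negative, seropositive contacts are still reported.
- State how missing Day 0 serology is handled.
- Say in 13.1 which contacts the 25% to 40% and 5% rates describe, and that power depends on entry seroprevalence.

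The serum is already collected, so the cost is wording plus a somewhat smaller primary sample: 74.8% power with 50 per arm or 69.5% with 44 at 25% vs 5%. That is slightly better than leaving seropositives in, but it does not restore 80.1%; doing so would take more enrollment than the planned 164. The amendment should be made before outcome data by arm are examined.

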3.3 Secondary objective

3.3.1 Prevention cohort

3.3.1.1 To estimate time to onset of signs and symptoms consistent with COVID -19 (e.g., fever, generalized body aches, cough, and shortness of breath)

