8.4. Administration of Flu-PRO Questionnaire

Participants will be assessed to determine the presence or absence of symptoms consistent with COVID-19 using the CDC defined COVID-19 symptom check list daily. In addition, Flu-PRO, a validated, standardized patient-reported outcome (PRO) symptom scale that comprehensively assesses the symptom experience in acute respiratory symptoms across multiple body systems will be used at enrollment and days 1-14 and 28. This will provide an opportunity to assess for potential symptoms related to Lambda as well as COVID-19.

For remote visits, FLU-PRO will be collected directly in REDCap through a link embedded in the

eMocha app. Participants will include their eMocha app username and cell phone number on the survey. For participants who are unable to access or use eMocha, surveys will be interviewer administered over the phone by trained research staff.

A validated, standardized patient-reported outcome (PRO) symptom scale that comprehensively assesses the symptom experience in influenza across multiple body systems was reported in 2016 by Powers and colleagues at the National Institute of Allergy and Infectious Diseases [18]. The purpose of the InFLUenza Patient-Reported Outcome (FLU-PRO[©]) measure is to comprehensively assess the presence and severity of influenza symptoms across body systems often affected by these viruses. The instrument was created in accordance with drug development recommendations of the US Food and Drug Administration (FDA) [19]. This new instrument yields a profile of scores across six body systems with a total score reflecting overall symptom severity. The questionnaire instructs respondents to rate the severity of 37 influenza symptoms over the past 24 hours, including those related to the nose, throat, eye, chest, head, stomach, fatigue, and body aches/pains. Six items measured the same symptom using different wording in order to select the best performing item for the final instrument. For 32 of 37 items, respondents rated the severity of each symptom on 5-point Likert-type scales from 0 (“Not at all”), 1 (“A little bit”), 2 (“Somewhat”), 3 (“Quite a bit”), to 4 (“Very much”). For the five remaining items, severity is expressed as frequency of occurrence: vomiting or diarrhea (0 times, 1 time, 2 times, 3 times, or 4 or more times), and sneezing, coughing, and coughed up mucus or phlegm on a scale from 0 (“Never”) to 4 (“Always”), with higher scores indicating more severe symptoms.

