8.11. Upper respiratory specimens for SARS-CoV-2 assessment

All participants in Group A Prevention cohort with onset of symptoms consistent with COVID-19 will be referred for clinical testing of upper respiratory samples for evidence of SARS-CoV-2.

All persons who remain asymptomatic will have study testing with upper respiratory samples for evidence of SARS-CoV-2 at study day 7, 14, and 28. When onsite visit for Day 28 is not on the exact Day 28, the study team will make every effort to have the upper respiratory specimens self-collected Day 28 at the participant's residence.

Specimens obtained will depend on site of collection and availability of swabs. Mid turbinate samples will be collected using a nylon flocked swab using the following steps: 1) inserting the swab into the nose in the horizontal position until gentle resistance is met, 2) leaving the swab in for 10-15 seconds then, rotating the swab, 3) repeating in the other nostril with the same swab. Specimens collected with nasopharyngeal swabs will be done according to standard instructions. The swab will be inserted into the nostril parallel to the palate. The swab should reach a depth equal to the distance from nostrils to outer opening of the ear. The swab will be left in place for several seconds to absorb secretions. The swab will be slowly removed from the nostril while rotating it.

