8.15. Adverse Event Evaluation

An AE is any untoward medical occurrence in a clinical study participant administered a medicinal (investigational or non-investigational) product. An AE does not necessarily have a causal relationship with the intervention. An AE can therefore be any unfavorable and unintended sign (including an abnormal finding), symptom, or disease temporally associated with the use of a medicinal (investigational or non-investigational) product, whether or not related to that medicinal (investigational or non-investigational) product (Definition per ICH).

This includes any occurrence that is new in onset or aggravated in severity or frequency from the baseline condition, or abnormal results of diagnostic procedures, including laboratory test abnormalities.

All adverse events, both serious and nonserious, will be collected from the time of informed consent through protocol Day 28. Participants will be asked open-ended and non-leading questions to evaluate for adverse events. Participants will also be asked directed questions to evaluate the presence or absence of fever, chills, arthralgia, myalgia, or pain. To monitor for injection site reactions, participants will be asked directed questions regarding pain, erythema, induration, or pruritus. The injection site will be inspected via video check-in on Day 7.

Adverse events will be collected directly in REDCap though a link embedded in the eMocha app. Participants will include their eMocha app username and cell phone number on the survey. For participants who are unable to access or use eMocha, surveys will be interviewer-administered over the phone by trained research staff.

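### The Group A symptom-onset outcome requires no confirmed infection, so symptoms from other causes dilute it, and it would be biased against Lambda if Lambda causes fever or generalized body aches

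*Combined protocol and SAP*

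**What the plan says.** The synopsis lists as the first Group A secondary outcome "Time to onset of signs and symptoms consistent with COVID -19 (Symptoms: Cough, sore throat, generalized body aches and shortness of breath", followed by "Signs Fever >100.4 F, RR >25, SpO2 <95% on room air". Section 3.3.1 sets the matching objective: "To estimate time to onset of signs and symptoms consistent with COVID -19 (e.g., fever, generalized body aches, cough, and shortness of breath". Neither text asks for a positive PCR or serology, gives a rule for attributing a symptom to infection or to the injection, or excludes a period after dosing.

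No later section supplies the missing condition. Section 12 defines only the two primary endpoints. Section 13.2.2 specifies secondary survival analyses for time to infection and time to clearance, not for symptom onset.

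The plan does look for drug-related symptoms. Of the Flu-PRO questionnaire, section 8.4 says: "This will provide an opportunity to assess for potential symptoms related to Lambda as well as COVID-19". Section 8.15 has participants asked "directed questions to evaluate the presence or absence of fever, chills, arthralgia, myalgia, or pain" as part of adverse event collection.

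Section 11 says the identified risks of Lambda "include hepatobiliary toxicity (transaminase elevations with or without hyperbilirubinemia) and injection site reactions". Fever and myalgia appear in neither its identified nor its potential risks.

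On testing, section 8.11 says that Group A participants "with onset of symptoms consistent with COVID-19 will be referred for clinical testing of upper respiratory samples". The result is not tied to the symptom outcome.

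**The concern.** Group A is PCR negative at entry, and section 13.1 expects only 5% of the Lambda arm to become infected. Most people in that arm who report a listed symptom for a reason other than COVID-19 would therefore be uninfected, yet each would be scored as having developed the illness the drug is meant to prevent.

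Two things follow. Background symptoms, equally common in both arms, shrink the contrast and cost power. Lambda-caused symptoms, if there are any, would add events to one arm only. Symptoms are screened daily from Day 1 after the single Day 0 injection, so reactions soon after dosing would enter a time-to-onset analysis as early events. The outcome could then show little or no clinical benefit, or an apparent harm, when infection had in fact been reduced.

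**Working it through.** **Inputs from the documents** (section 13.1): placebo infection p = 25% to 40%; Lambda infection 5%; 1:1 allocation; 110 individuals, or an effective 55; two-sided alpha 0.05.

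**Assumptions not in the documents:** a fraction s = 60% of infections is symptomatic; background symptoms b = 5% in each arm; Lambda-caused qualifying symptoms a = 0 to 20%. The three causes are taken as independent. The documents state neither an event rate nor power for this outcome.

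**Reproducing the plan's figures.** Exact power of the two-sided Fisher test against 5% on Lambda, by full binomial enumeration:
- 55 per arm: 80.1% at 25% placebo infection and 99.6% at 40%.
- 27 per arm: 36.1% and 84.0%.

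All four cells of the table in section 13.1 match, so the same method is used below at 55 per arm.

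**Formulas**
- Confirmed illness: p × s on placebo, 0.05 × s on Lambda.
- Unconfirmed, placebo: 1 − (1 − p × s)(1 − b).
- Unconfirmed, Lambda: 1 − (1 − 0.05 × s)(1 − b)(1 − a).

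**Confirmed illness**
- p = 25%: 0.25 × 0.6 = 15.0% v 0.05 × 0.6 = 3.0%; power 46%.
- p = 40%: 0.40 × 0.6 = 24.0% v 3.0%; power 89%.

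**Unconfirmed, placebo arm**
- p = 25%: 1 − 0.85 × 0.95 = 19.3%.
- p = 40%: 1 − 0.76 × 0.95 = 27.8%.

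**Unconfirmed, Lambda arm:** 1 − 0.97 × 0.95 × (1 − a), with power to show benefit:

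| a | Lambda arm | Power, p = 25% (placebo 19.3%) | Power, p = 40% (placebo 27.8%) |
|---|---|---|---|
| 0% | 7.9% | 31% | 72% |
| 2% | 9.7% | 20% | 60% |
| 5% | 12.5% | 10% | 43% |
| 10% | 17.1% | 3% | 20% |
| 20% | 26.3% | 0.1% | 2% |

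The row a = 0 isolates dilution. Background symptoms alone cost 46 − 31 = 15 points at 25% and 89 − 72 = 17 points at 40%.

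**Where the direction turns.** Setting the two unconfirmed proportions equal, the background term cancels and a = 1 − (1 − p × s)/(1 − 0.05 × s).
- p = 25%: 1 − 0.85/0.97 = 12.4%.
- p = 40%: 1 − 0.76/0.97 = 21.6%.

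At a = 20% the comparison is therefore 19.3% v 26.3% at p = 25%, which is reversed, with a 9.5% chance of a significant result against Lambda. At p = 40% it is 27.8% v 26.3%, not reversed, and that chance is about 1%.

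**Sensitivity to s.** If half of infections are symptomatic, the turning points are 10.3% (p = 25%) and 17.9% (p = 40%). If all are, they are 21.1% and 36.8%.

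**The case against.** A reader might infer that the outcome is biased against Lambda as a matter of fact. The documents do not support that. They give no rate of Lambda-caused fever or body aches, and section 11 lists neither. Section 4 describes limited receptor expression on muscle, blood-forming and nervous tissue, and better tolerability; that is a comparison with other interferons, so it does not rule reactions out. Section 8.4 speaks of an opportunity to look for potential symptoms, and the adverse event questions in section 8.15 are not confined to one arm. Looking for an effect is not predicting one. This objection stands, so the bias must be stated conditionally. The dilution does not depend on it.

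A reader might also infer that a real benefit would be reversed. That depends on the scenario, as the turning points show.

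Nor is the trial's main efficacy conclusion at risk. The primary endpoint is defined by PCR or new antibodies, and the survival analysis concerns time to infection. The symptom objective is one of estimation, with no test or power stated, so the power figures measure lost information and do not describe a planned analysis. They also ignore timing and household clustering.

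Two smaller points stand. The text specifies a fever threshold and generalized aches, and never says that a single item suffices. And a referral for clinical testing does not guarantee a completed or captured test.

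Symptoms of any cause are a legitimate outcome when reported beside a confirmed one. That does not close the gap, because the plan defines no confirmed one.

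**Conclusion.** The gap in the definition is real and nothing later in the plan closes it. As written, non-COVID symptoms count as COVID-19 onset in Group A. The certain part is dilution: about 15 to 17 points of power if 5% of each arm has background symptoms. The conditional part is bias against Lambda, which needs an excess of fever or generalized body aches that the documents neither quantify nor list as a risk. Under the stated assumptions, a 5% excess leaves 10% to 43% power across the plan's placebo range, against 46% to 89% for confirmed illness. Reversal needs an excess of about 12% at the low end and 22% at the high end. The point concerns one secondary outcome without a power calculation, so it should be corrected but does not threaten the primary analysis.

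**What to change.** Define the Group A outcome as time to the first listed sign or symptom in a participant whose SARS-CoV-2 infection is confirmed by study or clinical PCR, or by new antibodies, by Day 28. Keep all Group A participants in the denominator. State whether one listed item is enough.

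Add a prespecified window linking the symptom to the positive PCR, and a stated rule for cases confirmed by serology alone. Without the window, a Day 1 reaction in someone who tests positive on Day 14 would still be scored as COVID-19 onset on Day 1.

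Report symptoms of any cause by arm as a supportive and tolerability outcome, and name the analysis for symptom onset in section 13.2.2.

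The cost is wording plus capture of the referred clinical test results. The tests are already planned: referral of symptomatic participants, scheduled swabs for those without symptoms, and serology at entry and Day 28. The downside is fewer events. Symptomatic infections missed by both PCR and serology would not be counted, nor would those whose referred test is not completed and which serology also misses.
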